6.3 Data Relevance

Please see Section 2

6.4 Data Coding

Data analysis plan for focus groups. Video recorded focus groups will be analyzed using Max QDA, a qualitative data analysis software that enables seamless coding of text, video and picture based media. Qualitative analysis will proceed using Corbin and Strauss' constant comparative method. This method involves several coders ($n=3$), breaking down the data into discrete units and coding them to categories that reflect the language and concepts of the study participants. Weekly coding meetings will occur to discuss coding progress. Disagreements will be discussed until resolved.

6.5 Data Analysis Tools

MaxQDA for Focus groups

Statistical packages for survey and intervention (e.g., SAS, SPSS, R)

6.6 Data Monitoring

Redcap will be enabled to allow participants to skip questions (non-response option available) but they cannot advance through unless a choice is made. This will eliminate missing data while ensuring participants the ability to skip questions they do not want to answer. Incomplete surveys will be mitigated by survey creation to keep the survey short, use known presentation methods to ensure usability, comprehension and comfort reading. Missing data will be assessed and managed using standard procedures.

Verbatim transcripts will be produced from the focus groups.

7 - Data Handling and Record Keeping

7.1 Subject Data Confidentiality

Survey: Will be completed without collection of identifying information (names, contact, IP address). Electronic gift cards will be issued after completion of the survey to an email address provided by the participant and will not be linked to the data collected.

Focus group: we will use pseudonyms for the recorded VCU ZOOM focus groups

No link between the focus group participant PHI and data will be made. We will not keep a key that links the pseudonym with the demographic data collected.

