4.4 Recruitment Procedures

Recruitment Procedures Survey:

Recruitment will use a multipronged approach including community advertising, social media, word of mouth and leveraging of our community partners.

1.) Onsite at barbershops, Health Living and Learning Center (HLLC) and other community partner sites: Supervised by the research team, graduate and undergraduate students will be introduced to community partners and trained to introduce the study to potential participants who visit partnership businesses and organizations across the City of Petersburg. Project personnel will have a regular, weekly presence at each community partner site to build recognition and recruit to the survey.

- 2.) Additional recruitment pathways include distribution of study advertisements. These will be posted physically at various community locations and include a URL and QR code that enable access to the survey. We will also leave study information postcards (same URL and QR code) for distribution by community partners. We will also ask community partners with email lists, regular newsletters and other similar distribution lists to send out information about the study on their listservs.
- 3.) Social Media: distribution of study and survey advertising (including a link to the survey) using various social media platforms(e.g., direct recruitment via Facebook ads, posting information on VCU, VSU, and community partner social media accounts).
- 4.) Referral of friends (snowball) participants who complete the survey will have the option of completing a quick and seamless electronic recommendation for friends or family to consider participating.
- 5) Clinic partners. We have partnered with CVHS which has 4 clinics in the Petersburg city and surrounding counties. We will advertise in the clinic waiting rooms, staff at the clinics will hand out flyers for the study, and we will use any newsletters distributed by the clinic including playing our video on the television in the waiting rooms and sending invites to learn more via the text messaging system the clinic uses to distribute public health information, updates and health messages.

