5.4 Study Procedures

Survey

The survey will be a self-administered electronic survey (e-survey) expected to take 15-20 minutes to complete. Using a secure HIPAA compliant VCU Redcap survey housed on a VCU server, a unique survey link will be provided to interested participants (via email or QR code available on flyers and social media messaging). The secure, unique link will include a screener to determine eligibility, a self-administered information form with consent elements followed by the survey. Participants who complete surveys will receive an electronic gift card of \$20 sent to an email provided by the respondent.

Focus Groups:

Local barbers currently working in a Petersburg or Richmond Barbershop; will be recruited for focus groups. Barbershops are an excellent way to gain intervention 'reach' among our target population, Black men. Barbers within the Petersburg area will be recruited from one of the four community partner barbershops that agree to participate in the study. Barbers will be approached in-person at the shop by a member of the research team) who will visit shops to introduce the study and ask permission to leave study information and/or come back to talk to the group. Focus groups will be conducted virtually using smartphone accessible VCU Zoom and will be video recorded, with permission. Participants will engage in a 60-90-minute discussion.

Aim 3 Intervention:

Men will be invited to participate using all methods outlined above. Men who are interested will be directed to download the app to their personal device. Once the app is downloaded participants are able to self-direct through the screening process. If requested, a study member can assist with downloading the app and navigating through to the study screener.

Potential participants will be asked to complete a screener to ensure all eligibility criteria are met. Those who do not meet eligibility will be thanked for their time and navigated to an exit screen. For those who are eligible, they will next be asked to complete the consent process. After they consent, they will be navigated to the baseline questionnaire. Once completed, they will be able to access all other content (videos, infographics, request link to receive a call from screening navigation, additional surveys for values elicitation).

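### Aim 1 survey: a shared public link that pays $20 per completion, with no planned check for repeat or ineligible entries and no way to trace a repeated payment email to its record

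*Combined protocol and SAP*

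**What the plan says.** **Payment.** Section 5.4: "Participants who complete surveys will receive an electronic gift card of" $20, sent to an email address that the respondent supplies.

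**Access.** Section 4.4 says of the advertisements: "These will be posted physically at various community locations and include a URL and QR code that enable access to the survey". It adds: "We will also leave study information postcards (same URL and QR code) for distribution by community partners". The social media route is "distribution of study and survey advertising (including a link to the survey) using various social media platforms". Section 4.4 also lists on-site recruitment by project personnel, partner mailing lists, referral by friends and clinic partners.

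**The stated safeguard.** Sections 5.4, 5.7 and 7.3 say that "a unique survey link will be provided to interested participants (via email or QR code available on flyers and social media messaging"). On eligibility, section 5.4 says: "The secure, unique link will include a screener to determine eligibility". The survey is self-administered, and no verification of age, race, residence or cancer history is described.

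**Confidentiality.** Section 7.1 reads: "Will be completed without collection of identifying information (names, contact, IP address). Electronic gift cards will be issued after completion of the survey to an". The same section keeps the payment email unlinked to the survey data.

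**Data checks.** Section 6.6 (Data Monitoring) deals with skipped items, incomplete surveys and missing data. Section 7.2 (Data Quality Assurance) only refers back to earlier text. Neither mentions duplicate or invalid entries.

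**The concern.** A code printed on a poster or postcard is the same for everyone who scans it and can be scanned again. Each further completion earns another $20, and the only gate is a screener that the respondent answers about himself. The single-person link that the protocol appears to rely on therefore does not exist on the public routes.

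If staff notice one email address claiming several cards, they can decline to pay. They cannot tell which survey records came from that person, because section 7.1 rules out both the IP address and the link between email and record.

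At stake are the Aim 1 associations (section 3.2) and the interaction on which the survey was sized (section 6.1). Repeat entries counted as separate men make standard errors too small. Entries by people outside the population, or with made-up answers, weaken real associations. Section 2.2 says the survey informs the tailoring of the intervention, so errors would carry into the later aims.

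**Working it through.** **1. The plan's own figures.** Section 6.1 needs 175 men and adds a 20% buffer: 175 × 1.20 = 210, which reproduces. The buffer is for people who start but do not finish, so nothing is set aside for invalid entries. The stated 80% power cannot be reproduced, because screening prevalence, predictor scales and main effects are not given. With standard-normal predictors and a one-sided 5% test, simulation gives about 67–74% power if 0.38 is the log-odds coefficient, and about 98–99% at an odds ratio of 2.01.

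**2. What each control can do.**
- Unique link: can be personal only where sent individually by email; not on posters, postcards or social media.
- Screener: self-declared, inside the same link.
- Payment email: can reveal a repeated claim, but cannot point to a record.
- Sections 6.6 and 7.2: no check on duplicates or validity.

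**3. Exact repeats (illustration).** The shares and copy counts are assumptions; the documents give none. Suppose each repeater adds two extra copies. If a man is counted w times, the true variance exceeds the model's by about Σw² / Σw, and the one-sided error becomes P(Z > 1.645 / √(Σw²/Σw)).
- About 10% extra copies: 9 repeaters, 18 copies, 175 − 18 = 157 distinct men. Σw = 148 + 9×3 = 175; Σw² = 148 + 9×9 = 229; ratio 1.31, root 1.144. P(Z > 1.438) = 7.5%.
- About 20%: 17 repeaters, 34 copies, 175 − 34 = 141 distinct men. Σw = 124 + 17×3 = 175; Σw² = 124 + 17×9 = 277; ratio 1.58, root 1.258. P(Z > 1.308) = 9.5%.

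Simulation of the one-sided interaction test gives about 7% and 10%, against a nominal 5%. The result depends on the copy count: at the same shares, one extra copy per repeater gives about 7% and 9%, and four extra copies about 9% and 12%.

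**4. Outcomes unrelated to the truth (illustration).** This uses one standard-normal predictor, n = 175 and a true odds ratio of 0.50 per SD. If a share f of outcomes is random, the log odds ratio shrinks by roughly (1 − f), so the estimate is near 0.50^(1−f): 0.54, 0.57 and 0.62 for f = 10%, 20% and 30%. Simulation gives a mean estimate of 0.49 with clean data, then about 0.53–0.54, 0.58 and 0.62.

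**5. Power of the planned interaction with random-answer entries.** At 10%, 20% and 30%, power falls from about 74% to 69%, 56% and 49% (coefficient 0.38), or from about 99% to 97%, 93% and 85% (odds ratio 2.01).

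**The case against.** A reader might infer that repeat or ineligible entries can be neither prevented nor removed under this protocol. The documents do not support that. Section 7.1 bars certain identifiers and the email link. It does not bar checks that use only the anonymous record, such as completion time, internal consistency or identical answers across scales. Exact copies, which drive the error inflation above, are the easiest to find this way, since section 5.8 includes a 16-item and a 21-item scale. Checking payment emails before cards go out would also limit the incentive. These checks are possible; they are not planned.

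Nor do the documents show that invalid entries occurred, or that every entry arrives by a public code. Supervised on-site recruitment and emailed links are also described.

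The anonymity is deliberate. The consent waiver requested in section 4.8 rests on it, and sections 1.1 and 3.1 describe medical mistrust in this population. This stands as a reason to keep the answers anonymous and to count the cost of asking for an email earlier. It does not explain why no duplicate or validity procedure is stated.

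The simulations rest on assumed shares, and the odds-ratio illustration uses a single main effect rather than the planned interaction. They show direction and rough scale only.

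**Conclusion.** The concern holds in a limited form. On the public routes the link is not unique to a person, eligibility is self-declared, and no method is stated to prevent, detect or exclude repeat or ineligible paid entries. A repeat found through the payment email cannot be traced to its record. This is more than a missing detail, because the shared code defeats the safeguard that the protocol names.

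The size cannot be known from the documents. Under the assumed shares of 10% to 20% exact repeats, the effect is moderate: a 5% one-sided error of about 7% to 10%. Random outcomes pull estimates towards no association. The point concerns the Aim 1 survey only, not the Aim 3 app intervention. It is a cheap improvement, best made before data collection, because records that are anonymous and already mixed are hard to separate.

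**What to change.** 1. Let the public URL and QR code open a short entry form that takes only an email address, rejects one already used, and issues a one-time survey link that is not stored with the answers. Keep the eligibility screener inside the survey. The documents do not describe this function, so confirm with the survey platform's administrators that it can be set up.
2. Fix an exclusion rule before analysis that uses only data inside the anonymous record: implausibly short completion time, identical response patterns across the multi-item scales, and internally inconsistent answers. Report the number excluded and repeat the analysis without exclusions.
3. Check payment emails for repeats before issuing cards. Do not make payment depend on record-level checks, and do not compare answers between the email form and the survey: both would need the link that section 7.1 forbids.
4. Use a ZIP code check only if that item is added to the survey and the residence criterion is reconciled. The Synopsis includes the surrounding counties; section 4.3 names Petersburg alone.
5. Amend sections 5.4, 5.7, 7.1 and 7.3 to match. Section 7.1 should also acknowledge that an email address is collected, though held apart from the answers.

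**Cost.** Platform configuration and an ethics amendment. Respondents take one extra step and give an email before the survey rather than after it, which may deter some men in a population with medical mistrust. A person with several email accounts could still repeat.

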7.2 Data Quality Assurance

See above

7.3 Data Storage/Security

The survey will be a self-administered electronic survey (e-survey) expected to take 15-20 minutes to complete. Using a secure HIPAA compliant VCU Redcap survey housed on a VCU server, a unique survey link will be provided to interested participants (via email or QR code available on flyers and social media messaging). The secure, unique link will include a screener to determine eligibility, a self-administered information letter outlining consent items followed by the survey.

7.4 Study Records

VCU Redcap and VCU secure servers will be used to store all study data. Only study personnel will have access to the study data.

7.5 Retention of Records

The records will be kept secured and for the length of time necessitated by funder/sponsor.

8 - Study Considerations

8.1 Research Personnel Training

All personnel will maintain CITI training and records will be kept by study coordinator.

[name] will oversee training of the focus group moderators.

8.2 Unanticipated Problems and Protocol Deviations

Will be reported to the IRB according to regulations.
